5.2.1 Randomization

Participants aged 65 to 79 will be randomized (1:1) to receive either aIIV3 or IIV3-HD using a permuted block randomization scheme stratified by Lead and Contributing Site(s) for a total of ≥704 subjects. In Year 1 there will be 2 sites (Duke and Boston) and in Year 2 there will be 3 sites (Duke, Boston, and Cincinnati). A separate permuted block will be allocated for ≥176 subjects who are age 80 or older, thus getting an overall N≥880. Additionally, the first ~100 patients at Duke who opt-in will be assigned to return on day 181 for an additional blood draw. The repeat vaccination sub-study in year 2 will use a convenience sample and will not require a 1:1 distribution of subjects into the two study arms, and may include Duke subjects in the waning immunity sub-study (i.e., those that consented to blood draw at Study Day ≥181). The project statistician will generate permuted block randomization schemes that will be uploaded to the Research Electronic Data Capture (REDCap) study database (Section 7.2). The randomization schedule will not be available to the study staff, so the next randomization allocation will not be known before randomization occurs. Following confirmation of study eligibility criteria during Visit 1, participant randomization will be through REDCap with treatment allocation recorded on the case report form (CRF) by unblinded research staff who administer the vaccine. Participants and study staff doing follow-up evaluations will not have access to the treatment allocation CRF to maintain blinding. In the event that REDCap is unavailable, manual

randomization will occur through the use of envelopes. The project statistician will prepare 20 envelopes per age group per site (total of 40 per site) that will use the same randomization strategy as the primary scheme embedded in REDCap. When an unblinded team member is informed of the age group, he/she will pull the next envelope in order. In order to capture the allocation per subject, a separate form in REDCap will be used by the unblinded personnel to add the assignment. A log will need to be kept at the site capturing these instances.

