The EQ-5D-5L is the new version of the EQ-5D that increases the levels of severity from three to five to significantly increase reliability and sensitivity while maintaining feasibility and reducing ceiling effects (Appendix J)^{30,31}. The descriptive system comprises 5 dimensions of mobility, self-care, usual activities, pain/discomfort, anxiety/depression. For each of these dimensions, there are 5 response levels: no problems, slight problems, moderate problems, severe problems, and extreme problems. The respondent is asked to indicate his/her health state by ticking in the box against the most appropriate statement in each of the 5 dimensions. This decision results in a 1-digit number expressing the level selected for that dimension. The digits for 5 dimensions can be combined in a 5-digit number describing the respondent's health state from 11111 as best health and 55555 as worst health. These numbers are converted to a Utility Index that ranges from -0.109 (worst health) to 1.000 (best health) for US specific values. The minimum clinically important difference ranges from 0.05 to 0.1 depending on health conditions being studied. The EQ VAS records the respondent's self-rated health on a 20 cm vertical, visual analogue scale with endpoints labelled 'the best health you can imagine' (100) and 'the worst health you can imagine' (0). The respondent marks an 'X' on the scale number to indicate how their health is 'today.' The minimum clinically important difference on the VAS is 8.

The EQ-5D-5L, EQ-VAS have several advantages for use in this study. The measure is applicable to a wide range of health conditions and treatments and provide a simple descriptive profile and a single index value for health status. It has been validated in US and international populations and in older adults^{29,32,33}. The measure is useful for monitoring the health status of patient groups at different moments in time and assessing the seriousness of conditions at

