The proportion and 95% exact binomial confidence interval of serious adverse events and events of clinical interest, as well as the total number of events, will be presented by site, vaccine group, severity, and relatedness. Listings of the serious adverse events will also be presented. This information will also be prepared for the subset ($N \geq 176$) of subjects 80 or older.

7.1.5 Primary Objective 3

- To compare the seroconversion rate for the H3N2 influenza A strain after aIIV3 and IIV3-HD in the full study population
 - Hypothesis: the seroconversion rate for the H3N2 influenza A strain in the full study population after aIIV3 will be non-inferior to IIV3-HD

This objective will be assessed using a one-sided non-inferiority test with the alpha level set at 0.025 and non-inferiority margin of 10%.

The null hypothesis is the allV3 H3N2 seroconversion rate is inferior to IIV3-HD seroconversion rate.

$$H_0: \text{allV3 H3N2 rate} - \text{IIV3-HD H3N2 rate} \geq 0.1 \text{ (10\%)}$$

The alternative hypothesis is the allV3 H3N2 seroconversion rate is non-inferior to IIV3-HD H3N2 seroconversion rate.

$$H_a: \text{allV3 H3N2 rate} - \text{IIV3-HD H3N2 rate} < 0.1 \text{ (10\%)}$$

The upper bound of the one-sided binomial confidence interval of the difference will be used to make this assessment.

7.1.6 Secondary Objective 1

- To compare the proportions of local and systemic reactions after allV3 and IIV3-HD in the full study population and by age-group (65-79 years and ≥ 80 years) (other than moderate/severe injection site pain in the full study population)

The proportions in the full study population will be conducted as for Primary Objective 1 using a non-inferiority test to determine if allV3 is non-inferior to IIV3-HD with a 5% non-inferiority margin. These secondary objectives will be conducted with a one-sided alpha at the 0.01 level to adjust for multiple comparisons. It is recognized that with 12 different assessments at the alpha 0.01 level (given the events are truly independent) we are allowing an 11.4% chance of making a type I error.

The age-group assessments will be assessed using standard two-sided 95% confidence boundaries of the difference in proportions between the groups. No formal statistical testing will be implemented for the age-group comparisons.

7.1.7 Secondary Objective 2

- To describe and compare changes in health-related quality of life after allV3 and IIV3-HD in the full study population and by age-group

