Each HRQOL instrument produces a summary score to measure health-related quality of life. The change in score from pre-vaccination (baseline, Visit 1) to post-vaccination (Day 3, Visit 2) time points will be compared within and between the two groups.

The Late-Life Disability and Function Instrument and Late-Life Disability and Function Instrument-Computer Adapted Test (Year 1 Only)

The function and disability sections scale raw scores are transformed to a 0 (worst health) to 100 (best health) scale. The changes from baseline will be assessed within vaccine group using a paired t-test for the function and disability outcomes. If normality assumptions are not met, the testing will be performed with a Wilcoxon signed-rank test. The Mann-Whitney U test (Wilcoxon rank-sum test) will be used to compare the difference scores from baseline between the two vaccine groups for the function and disability outcomes.

EQ-5D-5L and Visual Analogue Scale (VAS)

The EQ-5D-5L responses are converted to a Utility Index that ranges from -0.109 (worst health) to 1.0 (best health) using the US specific value sets (http://www.euroqol.org/fileadmin/user_upload/Documenten/Excel/Crosswalk_5L/EQ-5D-5L_Crosswalk_Value_Sets.xls). The EQ VAS has a range of 0 (worst health) to 100 (best health). The changes from baseline will be assessed within vaccine group using a paired t-test for the index values and VAS. If normality assumptions are not met, the testing will be performed with a Wilcoxon signed-rank test. The Mann-Whitney U test (Wilcoxon rank-sum test) will be used to compare the difference scores from baseline between the two vaccine groups for the index values and VAS.

These health-related quality objectives will be conducted with a two-sided alpha at the 0.01 level to adjust for multiple comparisons. It is recognized that with 12 different assessments at the alpha 0.01 level (given the events are truly independent) we are allowing a 11.4% chance of making a type I error.

The statistical tests described above will also be performed for the subset (N=176) of subjects 80 or older. This testing will be considered exploratory with an alpha level of 0.05 with no alpha adjustment.

7.1.8 Secondary Objective 3

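### Section 7.1.7 compares the arms on quality of life only by a rank-sum test on change scores, with no baseline or stratum adjustment and no between-arm estimate to set against the protocol's minimum important differences

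*Combined protocol and SAP*

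**What the plan says.** Secondary Objective 2 (Section 7.1.7) is worded "To describe and compare changes in health-related quality of life after allV3 and IIV3-HD in the full study population and by age-group". The quantity compared, within arms and between them, is the change from the Visit 1 baseline to Day 3.

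The between-arm method is given in these terms: "The Mann-Whitney U test (Wilcoxon rank-sum test) will be used to compare the difference scores from baseline between the two vaccine groups". This is stated once for LLFDI function and disability and once for the EQ-5D-5L index and the EQ VAS. Within each arm the plan uses a paired t-test, with a signed-rank test if normality fails. Between arms it goes straight to the rank test.

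On error control: "These health-related quality objectives will be conducted with a two-sided alpha at the 0.01 level to adjust for multiple comparisons". For subjects aged 80 or older the same tests are repeated as exploratory, at 0.05.

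Section 5.5.1 gives minimum important differences of 2.7 to 4.3 for LLFDI function, 16.7 for limitation, 7.8 for frequency and 0.05 to 0.1 for the EQ-5D-5L index. For the visual analogue scale: "The minimum clinically important difference on the VAS is 8". Section 7 does not refer to any of these values.

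Section 5.2.1 describes 1:1 allocation in permuted blocks stratified by site, with a separate block for those aged 80 or older. Section 5.1 has the baseline quality-of-life assessment done before vaccination.

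**The concern.** The objective is to describe as well as compare, and Sections 1.1 and 1.2 make quality of life part of the case for choosing between the two vaccines. A reader will want to know how large any difference between arms is and whether a clinically important one has been ruled out. A rank-sum p-value answers neither question. A non-significant result at the strict 0.01 level would leave open whether a difference as large as Section 5.5.1 calls important remains compatible with the data.

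A second, smaller matter is that a change score fixes the slope on baseline at 1. When the correlation between baseline and post-vaccination scores is below 1, estimating that slope usually gives a tighter comparison. The strata used for allocation are likewise left out of the analysis.

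**Working it through.** **The plan's own figure.** Section 7.1.7 computes one number, the chance of at least one type I error in 12 independent tests at 0.01: 1 − 0.99^12 = 0.1136, or 11.4%. It reproduces. No power or sample size is stated for quality of life.

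**Inputs from the documents.** At least 880 subjects, about 440 per arm (Section 7.1.1). LLFDI in Year 1 only: about 220 at Duke plus 170 at Boston = 390, about 195 per arm (Section 4.3). Two-sided alpha 0.01, z = 2.576. Minimum important differences as listed above.

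**Assumed inputs.** The documents give no SD and no baseline/post correlation (rho). Ranges used: rho 0.5 to 0.9; VAS SD 15 to 20; index SD 0.10 to 0.20; LLFDI function SD 10.

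**Precision.** With equal SD at both times:
- variance of a change score = 2·SD²·(1 − rho)
- residual variance in ANCOVA = SD²·(1 − rho²)
- ratio, ANCOVA to change = (1 + rho)/2

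| rho | ratio | saving in N |
|---|---|---|
| 0.5 | 0.75 | 25% |
| 0.7 | 0.85 | 15% |
| 0.9 | 0.95 | 5% |

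This compares ANCOVA with the mean change, so it only approximates a comparison with the rank-sum test.

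**Power at the stated minimum important differences** (normal approximation, change score against ANCOVA).
- *LLFDI function, 2.7 points, SD 10, rho 0.5, 195 per arm.* Change: SE = 10·√(2/195) = 1.013; 2.7/1.013 − 2.576 = 0.09; power 54%. ANCOVA: SD 10·√0.75 = 8.66, SE = 0.877; 2.7/0.877 − 2.576 = 0.50; power 69%. At rho 0.7: 81% against 88%.
- *EQ-5D-5L index, 0.05, 440 per arm.* Worst case in the assumed range (SD 0.20, rho 0.5): 87% against 96%.
- *EQ VAS, 8 points, 440 per arm.* About 100% for both, for SD 15 to 20 and rho 0.5 to 0.9.

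**Interval width.** The 99% half-width of an adjusted VAS difference is 2.576·SD·√(1 − rho²)·√(2/440). It runs from about 1.1 points (SD 15, rho 0.9) to 3.0 points (SD 20, rho 0.5), so it could readily be read against 8.

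**Simulation of the planned test itself.** VAS-like scores capped at 100 and rounded, mean 80, SD 15, 400 per arm, alpha 0.01:
- No effect: type I error about 1% for both methods.
- 3-point effect, rank-sum against ANCOVA with robust errors: 57% against 74% at rho 0.5; 96% against 98% at rho 0.8.
- 8-point effect: 100% for both.
- Heavy-tailed changes (t with 3 degrees of freedom, scale 4, 1-point shift, capped): about 56% against 35%, in favour of the rank-sum test.

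**Comparison within the plan.** Section 7.1.8 plans 95% intervals for between-arm differences in proportions and in GMTs. Section 7.1.6 uses a non-inferiority test based on a confidence bound, plus 95% intervals by age group. Quality of life is the only secondary objective with no between-arm interval.

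**The case against.** Much of the case for the plan stands.

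- *Validity.* The rank-sum test holds its level. In a blinded 1:1 trial, regression to the mean acts on both arms alike, so it costs efficiency and does not bias the comparison.
- *Baseline.* A reader might infer that the baseline score is thrown away. It is not: it enters every change score with a slope of 1. What is missing is its use as a covariate.
- *Power.* A reader might also infer a general, material loss of power. The documents give no SD, correlation or distribution to support that. A 3-point VAS effect is below the protocol's threshold of 8, where both methods have about 100% power. The EQ-5D-5L is repeated only two days after baseline, so a high correlation is plausible, and the gain at 0.9 is small. With heavy-tailed changes the rank test wins.
- *A smaller repair exists.* A Hodges-Lehmann shift or a mean difference in change, with an interval, would supply the missing estimate without a new model.
- *A fuller analysis plan is promised.* Section 7 calls itself a summary, and the comprehensive plan could add an estimate.

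The last point does not remove the concern. Section 7.1.10 expressly defers only the exploratory analyses, while Section 7.1.7 already fixes the quality-of-life test and its alpha. None of these arguments supplies a difference that can be compared with Section 5.5.1.

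**Conclusion.** The point holds in this form: the between-arm quality-of-life test is valid, but it uses neither baseline as a covariate nor the randomisation strata, and no between-arm difference with a confidence interval is planned. The second omission carries the point. It follows from the text alone and depends on no assumption.

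The precision argument is supporting only. It assumes roughly normal scores and equal SDs at the two times, and its size depends on a correlation that the documents do not give. It has practical weight mainly for LLFDI function in Year 1, and a heavy-tailed pattern of change could reverse it. The documents do not support a claim of bias, of inflated type I error, or of inadequate power on the EQ VAS.

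This is a cheap improvement to a secondary analysis, not an error that threatens the trial's conclusions.

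**What to change.** In Section 7.1.7, and in the comprehensive analysis plan, add as the between-arm estimate for each instrument an ANCOVA of the post-vaccination score on vaccine group, adjusted for baseline score, site and age group, with robust or bootstrap standard errors. Report the adjusted mean difference with a 99% interval, matching alpha 0.01, beside the minimum important differences in Section 5.5.1. Keep the rank-sum test on change scores alongside it, as protection against heavy tails and ceiling effects.

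The cost is a few sentences of text and a few lines of code, using data and strata the trial already has. The one downside is a mean-based model on a bounded score, which the robust errors and the retained rank test largely cover.

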2.2 Study Outcome Measures

Where possible, all outcome measures will be evaluated and compared between the two treatment groups for the full population and in both age subsets (65-79 years and ≥ 80 years)

2.2.1 Primary Outcome Measures:

1. Comparison of the proportion of subjects reporting moderate/severe injection site pain within the first week post-vaccination in both treatment groups.
2. The frequency and descriptions of serious adverse events and adverse events of clinical interest observed in the two treatment groups.

3. H3N2 HAI seroconversion: The proportion of subjects achieving H3N2 seroconversion at day 29 (an HAI titer \geq 1:40 at day 29 if the baseline titer is $<$ 1:10 or a minimum four-fold rise in HAI titer if the baseline titer is \geq 1:10) in the respective season's vaccine.

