2.2.2 Secondary Outcome Measures

1. Comparison of local and systemic reactions within the first week post-vaccination in both treatment groups.
2. Change in scores on the Late Life Function & Disability Instrument (Year 1 only), EuroQOL 5 dimensions-5 level (EQ-5D-5L) and EuroQOL visual analogue scale (EQ VAS) pre-vaccination and post-vaccination will be compared between the vaccination groups and age groups.
3. HAI titers by vaccination group and age group (except for seroconversion to H3N2 strain for the full study population):
 - a. The proportion of subjects achieving seroconversion at day 29 (an HAI titer \geq 1:40 at day 29 if the baseline titer is $<$ 1:10 or a minimum four-fold rise in HAI titer if the baseline titer is \geq 1:10) for H1N1 and influenza B and H3N2 (by age group only) in the respective season's vaccine
 - b. Proportion of subjects with a seroprotective HAI titer (\geq 1:40) pre- and post-immunization at day 29 for each IIV antigen in the respective season's vaccine
 - c. The geometric mean HAI titer (GMT) for each IIV antigen in the respective season's vaccine

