6 LABORATORY ANALYSES

6.1 Influenza Hemagglutination Inhibition (HAI) Assay

Influenza Hemagglutination Inhibition (HAI) Assays will be performed on sera collected, contingent on additional funding. Briefly, reference wild-type, reassortant, or vaccine virus strains representative of the specific viral antigens included in the 2017-2018 and 2018-2019 influenza vaccine will be used to evaluate the relative levels of all three influenza strain-specific antibodies in participant serum samples collected pre- and 28 days post-vaccination from all study participants and at 181 days post-vaccination in a subset of 100 participants at Duke. To accomplish these activities all participant samples will be interrogated for influenza antibodies against the strains of interest using the influenza hemagglutination inhibition assay (HI). This assay is considered the “gold-standard” measure by which to evaluate seroconversion/seroprotection in response to seasonal influenza vaccination. This assay will be performed in accordance with the Duke Regional Biocontainment Laboratory Virology Unit's fully optimized and approved SOP (RVUSOP004 Influenza HI of Serum Samples). Briefly, test samples will be assayed by HAI as duplicate 2-fold dilution series starting at 1:10. Serum dilutions are then incubated with a concentration of virus verified to possess a known potential for red blood cell (RBC) agglutination. The presence of virus-specific antibodies is visualized via incubation of the virus-serum mixture with a RBC solution; the endpoint titer for a given dilution series is then expressed as the reciprocal of the final dilution in which complete HAI is observed. By convention, seronegative samples are defined as having an endpoint HAI titer < 40 and seropositive samples as having an endpoint titer of $\geq 1:40$; and seroconversion as a 4-fold change in endpoint titer relative to pre-immunization baseline or a change from <10 to $\geq 1:40$ ³⁷.

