To compare serum hemagglutination inhibition (HAI) antibody titers after aIIV3 and IIV3-HD for each of the three influenza vaccine strains contained in the respective vaccine for that season in the full study population and by age-group (except for seroconversion for the H3N2 strain in the full study population)

Responses to each influenza antigen will be analyzed, with the exception of seroconversion for H3N2, which is analyzed in Primary Objective 1. The proportion of subjects with seroprotection (pre- and post-immunization) seroconversion (4-fold rise from baseline) in the two treatment groups will be presented along with 95% exact binomial confidence intervals. A 95% confidence interval of the difference in proportions between the treatment groups will also be presented.

The GMTs for each influenza antigen, including H3N2, and 95% confidence boundaries will be presented for both treatment groups. A 95% confidence interval of the difference in GMTs between the treatment groups will also be presented. This information will also be prepared for the subset (N≥176) of subjects 80 or older.

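### Section 7.1.8 describes seroconversion without the 1:40 requirement that section 2.2.2 sets for baselines below 1:10, so secondary rates could depart from the defined endpoint

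*Combined protocol and SAP*

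**What the plan says.** The seroconversion rule appears in three forms.

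- **Sections 2.2.1 and 2.2.2 (and the Protocol Summary).** The primary outcome is "The proportion of subjects achieving H3N2 seroconversion at day 29". Two limbs follow: at least 1:40 on Day 29 if baseline is below 1:10, "or a minimum four-fold rise in HAI titer if the baseline titer is" 1:10 or more. Section 2.2.2 repeats both limbs in full "for H1N1 and influenza B and H3N2 (by age group only) in the respective season's vaccine".
- **Section 7.1.8 (Secondary Objective 3).** The analysis text for those secondary outcomes says only "seroconversion (4-fold rise from baseline". It has no 1:40 condition and no split by baseline.
- **Section 6.1 (HAI assay).** The laboratory text gives "seroconversion as a 4-fold change in endpoint titer relative to pre-immunization baseline or a change from <10" to at least 1:40. Its first limb is not limited to baselines of 1:10 or more, and it speaks of a change, not a rise.

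Section 6.1 also says that samples are run as a "duplicate 2-fold dilution series starting at 1:10". No section says what number a titre below 1:10 takes in the analysis. Section 7.1.5, the primary H3N2 analysis, restates no definition, so 2.2.1 governs it.

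**The concern.** The two-limb rule exists because a baseline below the first dilution has no measured value, so a fold rise from it cannot be computed. Requiring 1:40 for those subjects avoids the problem. The shorter wording in 7.1.8 brings it back: whether such a subject counts depends on a coding choice that the plan never states.

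Two things are at stake. First, the secondary seroconversion rates for H1N1 and influenza B, and for H3N2 by age group, could be computed under a rule other than the endpoint definition. Second, section 7.1.2 assigns the same Immunogenicity Population to Primary Objective 3 and Secondary Objective 3, and the two age groups (65-79 and 80 or older) partition it. H3N2 seroconverters by age should therefore sum to the primary count, and under two different rules they need not.

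**Working it through.** **The plan's own figure.** The only related number is the immunogenicity sample size in 7.1.1: 50% seroconversion in both arms, margin 10%, one-sided alpha 0.025, about 80% power, 390 per arm (780 in total).

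- n per arm = (1.960 + 0.842)² × (0.5×0.5 + 0.5×0.5) / 0.10² ≈ 393, or 786 in total.
- Power at 390 per arm = Φ(0.10/√(0.5/390) − 1.960) = 79.8%.

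The stated figure reproduces. It rests on an assumed 50% rate and does not change with the wording examined here.

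**Comparison of the rules.** Inputs: two-fold dilutions from 1:10 (section 6.1), the 2.2 rule, and the 7.1.8 rule read as Day 29 titre / baseline titre ≥ 4. The value for titres below 1:10 is not in the documents, so three assumptions are tried. All baseline/Day 29 pairs on the grid <10, 10, 20, ..., 1280 were compared.

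| Baseline → Day 29 | 2.2 rule | 7.1.8, <10 coded 5 | 7.1.8, <10 coded 10 | 7.1.8, no value |
|---|---|---|---|---|
| <10 → 10 | No | No (10/5 = 2) | No (10/10 = 1) | Not counted |
| <10 → 20 | No | **Yes** (20/5 = 4) | No (20/10 = 2) | Not counted |
| <10 → 40 | Yes | Yes (40/5 = 8) | Yes (40/10 = 4) | **Not counted** |
| <10 → 80 or more | Yes | Yes | Yes | **Not counted** |
| ≥10 → at least four-fold higher | Yes | Yes | Yes | Yes |

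All remaining pairs are non-responders under both rules.

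- Coded 5: one extra pair (<10 → 20) and none missed. The rate can only go up.
- Coded 10: no discordant pair.
- No value: no extra pair, but every <10 → ≥40 responder is missed. If those subjects stay in the denominator, the rate goes down.

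**Section 6.1, read as a rise.** It keeps the limb from <10 to ≥1:40, so it misses no responder under any coding. It differs from 2.2 only by the pair <10 → 20, and only if <10 is coded 5.

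**Size, illustration only.** With <10 coded 5, the overstatement equals s × q, where s is the share of subjects with baseline below 1:10 and q is the share of those at exactly 1:20 on Day 29. Neither is in the documents. If both are assumed to lie between 5% and 30%:

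- low end: 0.05 × 0.05 = 0.25 points; 0.0025 × 780 ≈ 2 subjects;
- high end: 0.30 × 0.30 = 9 points; 0.09 × 780 ≈ 70 subjects.

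The width of this range shows that no useful single figure can be given. With no value assigned, the understatement is s times the share of those subjects who reach 1:40, and that share is not given either.

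**With the 2.2 rule placed in both 7.1.8 and 6.1**, no discordant pair remains.

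**The case against.** The best defence is that 2.2.2 already gives the full rule for exactly the outcomes that 7.1.8 analyses. The parenthesis in 7.1.8 can then be read as shorthand, the more so because the introduction to section 7 calls its contents summary points and promises a comprehensive SAP. This stands in part: an analyst who follows 2.2.2 gets the right answer, so the rates could differ rather than must differ. It does not remove the point, because the text that describes the analysis states a different rule and nothing in the plan says which prevails.

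A second defence concerns scope. The body of 7.1.8 excepts H3N2 seroconversion without limiting the exception to the full population; only the objective statement does so. Placing H3N2 by age group under the 7.1.8 wording is therefore an inference. It is a reasonable one, since the objective includes that outcome and no other analysis section covers it. The body of 7.1.8 is also not carefully worded here: it refers H3N2 seroconversion to Primary Objective 1, which is injection-site pain, when Primary Objective 3 is meant.

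A reader might infer more than the documents support:

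- *That the shorter rule over-counts.* This holds only if titres below 1:10 are coded at 5 or less. The plan gives no value, and the other two treatments give no difference or an under-count.
- *That section 6.1 would count four-fold falls as seroconversion.* Taken literally, a change covers a fall, but the same section speaks of response to vaccination and 2.2 says rise. The reading is strained, and the word only needs tidying.
- *That the comparison between vaccines is biased.* Both arms would be scored by the same rule. If the misclassified share is similar in each, most of it cancels in the difference, and 7.1.8 reports confidence intervals without a test or margin.

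**Conclusion.** The point holds as a minor error. The wording in 7.1.8 drops a condition that 2.2.2 sets for the same outcomes, and 6.1 adds a third wording. Because titres below 1:10 have no assigned value, secondary seroconversion rates computed under 7.1.8 could be higher than, equal to or lower than those under the defined endpoint, and H3N2 counts by age group could fail to sum to the primary count. Neither the direction nor the size can be settled from the documents; the 0.25 to 9 point range rests wholly on assumed shares and on coding below 1:10 as 5. A reader might infer that the primary H3N2 result is at risk. It is not on this ground: 2.2.1 states the full rule for that outcome, 7.1.8 does not analyse it in the full population, and the sample size is unchanged.

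**What to change.** 1. In 7.1.8, replace the parenthesis with a reference to the two-limb definition in 2.2, and say that it applies to every strain and both age groups. Correct the reference for full-population H3N2 seroconversion to Primary Objective 3.
2. In 6.1, cite the same definition and replace *change* with *rise of at least*.
3. State once the numeric value used for titres below 1:10. The two-limb rule does not need it, but the geometric mean titres in 7.1.8 do.

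These are wording edits only. They need no new data and change neither the sample size nor the primary analysis. They should be made before the immunogenicity data are analysed, and carried into the comprehensive SAP.
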